# 3.4.1. Treatment Compliance

Study treatment compliance will be summarized descriptively as a quantitative variable, calculated as

$$\frac{\text{number of study treatment doses taken}}{\text{number of study treatment doses prescribed}} \times 100\%.$$

A study treatment dose is considered scheduled if KPT-9274 and/or niacin and/or nivolumab is scheduled. The number and percentage of patients with study treatment compliance ≥80% will be provided. Note that the number of scheduled study treatment doses does not include doses missed due to treatment interruption or other reasons not related to patient choice.

Treatment compliance will also be presented separately for KPT-9274, niacin, nivolumab as

$$\frac{\text{number of actual doses taken}}{\text{number of doses scheduled}} \times 100.$$

Similarly, the number of scheduled doses does not include doses missed due to treatment interruption or other reasons not related to patient choice. The number and percentage of patients with compliance  $\geq 80\%$  for each drug will be provided.

# 4. EFFICACY

Disease response will be evaluated according to RECIST 1.1 (advanced solid malignancies) or Lugano Classification (NHL) and will include the following endpoints: Time-to-event efficacy endpoints will be performed using the same Kaplan-Meier method for estimation of summary statistics, and will include the 25th, 50th (median) and 75th percentiles, associated two-sided 95% CIs (if estimable), and number of events and censored observations

# 4.1. EFFICACY ENDPOINTS

Please refer to Table 4-1 below for primary and secondary endpoints and the corresponding definitions

Table 4-1 Efficacy Endpoints and Definitions

Endpoint	Definition	
Secondary Endpoints		
Objective response rate (ORR)	Proportion of patients who have a response of partial response (PR) or complete response (CR)	
Duration of response (DOR)	The duration of time from first meeting CR or PR measurement criteria (whichever occurs first) until the first date that PD recurrence is objectively documented or death due to any cause	
	Please refer to Table 4-3 for details on the outcome and censoring definitions.	
Progression-free survival (PFS)	The duration of time from date of first study treatment until the first date that PD is objectively documented or death due to any cause.	
	Please refer to Table 4-2 for details on PFS outcome status (PFS event vs. censored) and censoring definitions.	
Overall survival (OS)	Duration from the date of first study treatment until death due to any cause. If death event did not occur during the follow-up period, the patient is censored at the date of discontinuation from the study (i.e. withdrawal of consent), or date of last participating visit (e.g., a telephone contact with patient status being alive) on or before database cutoff date, whichever occurs first.	
Time to Progression (TTP)	The duration of time from date of first study treatment until the first date that PD is objectively documented or death due to PD	

Disease control rate (DCR)	Proportion of patients who have a response of CR, PR, and Stable Disease (SD) ≥ 16 weeks.
Duration of disease control	Duration of disease control is defined among patients achieving disease control as the duration from the date of first meeting the response measurement criteria for disease control to the date of PD or death due to disease progression.  Please refer to Table 4-3 for details on the outcome and censoring definitions.

Table 4-2 PFS and DOR outcome and censoring definition

Situation	Date of event or censoring	Outcome
No baseline disease assessment	Date of first study treatment	Censored
No adequate post-baseline disease status assessment unless death occurs prior to first post-baseline assessment	Date of first study treatment	Censored
Death before PD without a gap of 2 or more consecutively missed scheduled disease status assessment before death	Date of death	Event
PD without a gap of 2 or more consecutively missed scheduled disease status assessment before progression	Date of PD	Event

 
No PD or death on or before
 
a. database cut,
 
b. withdrawal of informed consent,
 
c. lost to follow-up,
 
d. start of new antineoplastic treatment,
 
e. No PD or death before a gap of 2 or more consecutively missed scheduled disease status assessment
 
	Date of last adequate disease assessment on or prior to the earliest occurrence of the events (a. – e.) listed in the left column	Censored
whichever occurs first		

Table 4-3 TTP and Duration of disease control outcome and censoring definition

Situation	Date of event or censoring	Outcome
No baseline disease assessment	Date of first study treatment	Censored
No adequate post-baseline disease sassessment unless death due to dise progression occurs prior to first post-baseline assessment	ase	Censored
Death due to disease progression be PD without a gap of 2 or more consecutively missed scheduled dis status assessment before death		Event
PD without a gap of 2 or more consecutively missed scheduled dis status assessment before progression		Event
No PD or death due to disease progression on or before  a. Death due to reasons other t disease progression	han  Date of last adequate disease assessment on or prior to the earliest occurrence of the events (a. – f.) listed in the left column	Censored
b. database cut,		
c. withdrawal of informed con	sent,	
d. lost to follow-up,		
e. start of new antineoplastic treatment,		
f. No PD or death due to disea progression before a gap of more consecutively missed scheduled disease status assessment		
whichever occurs first		

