9. STATISTICAL METHODS

A statistical analysis plan (SAP) will be finalized prior to database lock. Any changes from the statistical analyses described in this document will be described in the SAP, and any deviation from the final SAP will be described in the final report.

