9.5. Efficacy Analysis

Disease response will be evaluated according to RECIST 1.1 (advanced solid malignancies) [Appendix 4](#)) or Lugano Classification (NHL) ([Appendix 3](#)) and will include the following endpoints: Time-to-event efficacy endpoints will be performed using the same Kaplan-Meier method for estimation of summary statistics, and will include the 25th, 50th (median) and 75th percentiles, associated two-sided 95% Cis (if estimable), and number of events and censored observations.

- Overall response rate (ORR): The analysis of ORR will be performed by calculating the point estimate of the percentage of patients who have either CR or PR, presented as the number and percentage of patients, including a two-sided 95% CI.
- Duration of response (DOR): the duration of time from first meeting CR or PR measurement criteria (whichever occurs first) until the first date that Progressive Disease (PD) recurrence is objectively documented. Patients without documented PD will be censored on the date of last disease assessment.
- Disease control rate (DCR): The analysis of DCR will be similar to that described for ORR, for patients who achieve CR, PR, or SD for ≥ 16 weeks.
- Duration of disease control: the duration of time from date of first study treatment until the first date the PD is objectively documented. Patients without documented disease progression will be censored on the date of last disease assessment.
- Progression-free survival (PFS): the duration of time from date of first dose of study treatment until the first date that PD is objectively documented or death due to any cause. Patients without documented PD will be censored on the date of last disease assessment.
- Overall survival (OS): the duration of time from date of first dose of study treatment until death from any cause. Patients who withdraw from the study or are alive at the time of data analysis will be censored on the date of last contact.

- TTP: The duration of time from date of first dose of study treatment to date of PD. Patients who withdraw from the study or are alive at the time of data analysis per Section 2.2.2 without documented DD will be censored on the date of last contact.

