#### 1.3. ENDPOINTS

# 1.3.1. Efficacy Endpoints

Disease response will be evaluated according to RECIST 1.1 (advanced solid malignancies and melanoma) or Lugano Classification (NHL) and will include the following:

- Objective response rate (ORR): proportion of patients who have a response of partial response (PR) or complete response (CR).
- Duration of response (DOR): the duration of time from first meeting CR or PR
  measurement criteria (whichever occurs first) until the first date that PD recurrence is
  objectively.
- Disease control rate (DCR): DCR proportion of patients who have a response of CR, PR, and Stable Disease (SD) ≥ 16 weeks.
- Duration of disease control: the duration of time from date of first study treatment until the first date that PD is objectively documented.
- Progression-free survival (PFS): the duration of time from date of first study treatment
  until the first date that PD is objectively documented or death due to any cause.
- Overall survival (OS): the duration of time from date of first study treatment until death from any cause.
- Time to Progression (TTP): The duration of time from date of first study treatment until
  the first date that PD is objectively documented or death due to PD.

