# 1.7. MODIFICATIONS TO THE STATISTICAL SECTION OF THE PROTOCOL

The current SAP is based on Protocol Version 5.0 dated 1 March 2020. No modifications were made to the statistical section of the protocol.

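### The SAP defines duration of disease control in two ways, sends DOR to the wrong censoring table, and declares no departures from the protocol although there are several

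*SAP*

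**What the plan says.** **Duration of disease control.** SAP 1.3.1 has "Duration of disease control: the duration of time from date of first study treatment until" documented PD, and protocol 9.5 has "the duration of time from date of first study treatment until the first date the PD is objectively documented". Neither names a subset of patients. SAP Table 4-1 differs: "Duration of disease control is defined among patients achieving disease control as the duration from the date of first meeting the response measurement criteria". There the interval ends at PD or death due to progression. Disease control means CR, PR, or SD lasting at least 16 weeks.

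**DOR.** Table 4-1 runs DOR "until the first date that PD recurrence is objectively documented or death due to any cause", then adds "Please refer to Table 4-3 for details on the outcome and censoring definitions". The DOR rules are in the other table, headed "Table 4-2 PFS and DOR outcome and censoring definition". Table 4-3 covers TTP and duration of disease control and censors deaths from causes other than progression. SAP 1.3.1 and protocol 9.5 give PD as the only DOR event.

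**Declaration.** Protocol 9 states: "Any changes from the statistical analyses described in this document will be described in the SAP". SAP 1.7 states: "No modifications were made to the statistical section of the protocol". SAP 1.8 says only that this is the first version of the SAP.

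**The concern.** Two programmers who follow the SAP literally could produce different Kaplan-Meier estimates from the same data. For duration of disease control, the start, the population and the event all differ between SAP 1.3.1 and Table 4-1. The Table 4-1 start is also ambiguous by itself: with scans every 8 weeks and a 16-week SD threshold, a stable-disease patient could first meet the criteria at Week 8 or at Week 16. For DOR, the table that the row cites reverses the event status of a responder who dies without PD from another cause.

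The declaration makes this harder to see. A reader who relies on SAP 1.7 would assume that the protocol's event rules, censoring dates and efficacy populations were applied.

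**Working it through.** The documents give no figure on this point, so there is none to reproduce. The check compares passages and sizes the differences by example.

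**1. One patient.** Inputs: 28-day cycles and scans on Day 1 of odd cycles (protocol Tables 1-3, footnotes 12 and 15). The Week 8 scan is Day 57, Week 16 is Day 113, and C9D1 is Day 8 × 28 + 1 = 225. Take SD at every scan until PD on Day 225.
- From first treatment (SAP 1.3.1): 225 − 1 = 224 days.
- Table 4-1, start at Week 8: 225 − 57 = 168 days.
- Table 4-1, start at Week 16: 225 − 113 = 112 days.

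**2. Medians.** Assumptions: exponential time to PD with median m weeks, PD recorded at the next 8-week scan, no CR or PR, no censoring, and SAP 1.3.1 read as all treated patients. Then P(recorded PD later than 8k weeks) = 0.5^(8k/m). Given no PD by the Week 16 scan, the time beyond Week 16 has the same distribution. The Table 4-1 median with a Week 16 start therefore equals the SAP 1.3.1 median, and a Week 8 start adds 8 weeks. Values of m that fall on a scan date are avoided, because the median is then not unique.

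| PD median m (assumed) | Share with disease control, 0.5^(16/m) | SAP 1.3.1 | Table 4-1, Week 8 start | Table 4-1, Week 16 start |
|---|---|---|---|---|
| 12 weeks | 39.7% | 16 | 24 | 16 |
| 28 weeks | 67.3% | 32 | 40 | 32 |

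**3. DOR.** Take a responder who dies without PD, from a cause other than progression, with no missed scans. Tables 4-1 and 4-2 count an event on the date of death. Table 4-3 censors at the last adequate assessment. Protocol 9.5 censors at the last disease assessment.

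To size this, let r be the hazard of such deaths divided by the PD hazard (assumed). With deaths as events, the event-free proportion is 0.5^(8k(1+r)/m) at scan k and 0.5^((8(k−1)+8kr)/m) just before it. With deaths censored, it is 0.5^(8k/m) at scan k.
- m = 28, r = 0.25. Deaths as events: 0.5^(22/28) = 0.580 just before Week 24 and 0.5^(30/28) = 0.476 at Week 24, so the median is 24 weeks. Deaths censored: 0.5^(24/28) = 0.552 at Week 24 and 0.5^(32/28) = 0.453 at Week 32, so the median is 32 weeks.
- m = 28, r = 0.10. Deaths as events: 0.5^(27.2/28) = 0.510 just before Week 32, so the median is 32 weeks under both rules.

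**4. Protocol section 9 against the SAP.**

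| Item | Protocol | SAP |
|---|---|---|
| DOR event | PD (9.5) | PD or any death (Tables 4-1, 4-2) |
| Duration of disease control | First treatment to PD, no subset (9.5) | New start, patients with disease control only, adds death due to progression (Table 4-1) |
| TTP censoring | Last contact (9.5) | Last adequate assessment (Table 4-3) |
| New antineoplastic therapy; two or more missed assessments | No rule in 9.5 | Censored (Tables 4-2, 4-3) |
| No baseline or no adequate post-baseline assessment | No rule in 9.5 | Censored at first treatment, with an exception for qualifying early deaths (Tables 4-2, 4-3) |
| OS censoring | Last contact (9.5) | Study discontinuation or last participating visit up to cutoff, whichever is first (Table 4-1) |
| Primary efficacy population, Parts A/B | Dosed at the RP2D chosen for expansion (9.3.1) | All treated (3.1.1) |
| Per-protocol base | ITT patients (9.3.2) | All patients (3.1.1) |
| Efficacy evaluable population | None | Added (3.1.1) |
| Early look | Futility rule (9.5.1) | No interim analysis (1.6), although SAP 1.1 repeats the futility rule |

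SAP 4.2 also lists a *duration of clinical benefit* that is defined nowhere, and it leaves TTP out of the same sentence.

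**The case against.** Several points on the other side stand.

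- The DOR pointer is very probably clerical. Table 4-1 and the Table 4-2 heading agree, and Table 4-3 does not name DOR.
- SAP 1.7 could mean only that the protocol text was not edited. Even so, SAP 1.8 lists no changes, so the requirement in protocol 9 is unmet on either reading.
- The move to all treated patients is largely a repair. Protocol 2.1.2 makes activity in the escalation phase an objective, which a set limited to the RP2D cannot serve, and protocol 9.3.2 already mentions an mITT population. It is still undeclared. The per-protocol change follows from it, and the efficacy evaluable set is only supportive.
- SAP 4 applies Kaplan-Meier summaries to time-to-event endpoints generally, so TTP is not left without a method.

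A reader might also infer more than the documents support.

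- The DOR sentence in SAP 1.3.1 breaks off and might seem to have lost a death clause. The protocol synopsis and 9.5 show that only the word *documented* is missing. Adding death there is a change, not a completion.
- Counting death due to PD in TTP might look like an SAP invention. It follows protocol 2.2.2, which conflicts with protocol 9.5.
- Protocol Table 10 might be used to state how many patients the population change affects. Table 12 gives different counts for 60 mg and 80 mg with niacin (11 and 5, against 10 and 6), and no RP2D is stated.
- A very long TTP censoring gap can be built from a patient who has calls but no scans for a year. Footnotes 15 and 19 require an end-of-treatment scan for non-progressors and plan 3-monthly scans where feasible, so that patient is not typical.
- A larger effect for duration of disease control appears if all treated patients are compared with disease-control patients timed from first treatment. No passage uses the second definition.

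**Conclusion.** The point holds on current text. The SAP has two incompatible definitions of duration of disease control, a wrong table reference for DOR together with a DOR event that differs from SAP 1.3.1 and protocol 9.5, and a declaration of no modifications that is not correct.

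The size is moderate. The start date alone changes an individual stable-disease value by 8 or 16 weeks, but the medians of the two SAP definitions differ by 0 or 8 weeks under the exponential assumption. For DOR, the any-death rule and the censoring rule give the same median or medians 8 weeks apart in the cases worked above. A 16-week gap (32 against 48) appears only with a PD median of 44 weeks and r = 0.50, that is, one third of first events being deaths without PD. The PD medians and r are assumptions, and the 8-week steps reflect the scan grid.

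The endpoints are descriptive, secondary in Parts A to C, and primary only in the expansion if it is conducted. No stated decision rule uses these medians. The correction should be made before the analysis is run, but the design is not in question.

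**What to change.** 1. **Duration of disease control.** Put one definition in SAP 1.3.1 and Table 4-1: from first study treatment to PD or death due to progression (Table 4-3), in patients with disease control. The start agrees with protocol 9.5, and protocol Appendix 4 also measures stable disease from start of therapy. The restriction is needed because without it the variable would duplicate TTP. Add a footnote that SD patients have at least 16 weeks by construction. This combination is a choice; the essential step is to state one definition and declare it.
2. **DOR.** Point the Table 4-1 row to Table 4-2, align SAP 1.3.1 to PD or death from any cause, and declare the change from protocol 9.5.
3. **SAP 4.2.** Replace *duration of clinical benefit* with TTP, or define it and name TTP as well.
4. **SAP 1.7.** Replace the sentence with a list of departures from protocol section 9, covering at least the table rows above. With fix 1, duration of disease control is entered for population and event only. For TTP, note that the event follows protocol 2.2.2 where 2.2.2 and 9.5 differ. State the new-therapy rule explicitly, because protocol 6.9.3 treats starting such therapy as an indication of progression. Reconcile SAP 1.6 with the futility rule in protocol 9.5.1.

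The cost is SAP wording only. DOR may be somewhat shorter than under protocol 9.5, because deaths count. Duration of disease control will be 8 or 16 weeks longer per SD patient than under the Table 4-1 start. As it covers only patients who reached disease control, its median must not be read as TTP.

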# 4.2. STATISTICAL METHODS FOR EFFICACY ENDPOINTS

Binary endpoints of ORR and DCR will be calculated by point estimate with a 95% confidence interval (CI) using the exact method.

For time to event endpoints of DOR, PFS, OS, duration of clinical benefit and duration of disease control, the number and percentage of patients who had an event will be reported.

Median event time with 95% CI will be summarized using Kaplan-Meier (KM) method. The KM curve for PFS will be provided by treatment arm.

# 5. SAFETY

Safety analyses will use safety population. Each tumor type will be analyzed separately with the outputs presented by part and cohort and for all patients combined.

Safety and tolerability of KPT-9274 will be evaluated by means of DLTs (dose escalation cohorts only), AE reports, electrocardiograms and laboratory safety evaluations.

#### General rules

All safety analyses will be performed using the following common rules:

- The baseline value is the last available value before the first dose of study treatment. Please also refer to Section 2.6 for additional information.
- The analyses of the safety variables will be essentially descriptive, and no statistical testing is planned.
- Unscheduled visit measurements will be used for computation of baseline, worst and last values. The unscheduled visit measurements will also be included in data listings.

# **5.1.** ADVERSE EVENTS

An AE is defined as any untoward medical occurrence in a patient receiving a pharmaceutical product regardless of a causal relationship with this treatment. An AE can therefore be any unfavorable sign and unintended sign (including an abnormal laboratory finding), symptom, or disease temporarily associated with the use of a study treatment, whether or not related to the study treatment.

All AEs (including serious adverse events [SAEs]) will be coded to a preferred term (PT) and associated primary system organ class (SOC) using the MedDRA.

The severity of all AEs will be graded according to the NCI CTCAE Grading Scale, Version 4.03. An AE with a CTCAE grade of 3 or higher is considered a severe AE. The severity of the AE is different from the seriousness of the AE. For AEs not covered by CTCAE, the severity will be characterized as "mild," "moderate," "severe", "life-threatening" (corresponding to Grades 1 to 4) according to the following definitions:

- Mild events are usually transient and do not interfere with the patient's daily activities.
- Moderate events introduce a low level of inconvenience or concern to the patient and may interfere with daily activities.
- Severe events interrupt the patient's usual daily activities.
- Life-threatening.

# 5.1.1. Definitions of Treatment-Emergent Adverse Events (TEAEs), Serious Adverse Events (SAEs), and Treatment-Emergent Treatment-Related Adverse Events (TRAEs)

# **5.1.1.1.** Treatment-Emergent Adverse Event (TEAE)

• Treatment-emergent adverse events (TEAE) of study treatment are defined as any event that was not present prior to the initiation of study treatment (KPT-9274 and/or niacin

and/or nivolumab) or any event already present that worsens in either intensity or frequency following exposure to study treatment, from the first dose of study treatment to 30 days after the last dose of study treatment inclusive, or the day before the start of a new antineoplastic treatment, whichever occurs first. Additionally, any AEs that occurred 30 days after the last dose of study treatment or after the start of a new antineoplastic treatment will also be considered as TEAE, if assessed by the Investigator as related to any drug of the study treatment.

# **5.1.1.2.** Serious Adverse Event (SAE)

An SAE is any untoward medical occurrence, at any dose, that:

- Results in death
- Is life-threatening (i.e., an event in which the patient was at risk of death at the time of the event; it does not refer to an event that hypothetically might have caused death if it were more severe)
- Requires inpatient hospitalization or prolongation of existing hospitalization
- Results in persistent or significant disability/incapacity
- Results in a congenital anomaly/birth defect

SAE needs to be clearly documented on the AE form. SAEs that occur at any time between the signing of the ICF up to the first dose of study treatment, must be reported (in addition to SAEs that occur after the first dose of study treatment).

